Among PFOA, PFOS, PFHxS and PFNA concentrations, water consumption had the strongest effect on PFHxS serum levels. In particular, water consumption had the highest effect on PFHxS serum levels among persons aged \leq 19 years (β = 0.31, SE = 0.15, marginal effect = 36.4%). Geometric mean PFOS and PFOA serum levels were also higher among persons who drank \geq 4 cups of water per day compared with those who drank <4 cups per day (NH DHHS 2016, Daly 2018). Linear trends were observed for geometric mean serum levels of PFOS, PFOA, and PFHxS and increasing time spent at the Pease Tradeport. The trend was strongest for PFOS and PFHxS (NH DHHS 2016, Daly 2018).

8

9 2.3 Selection of Sites

10 Possible candidate sites include communities whose drinking water was impacted by AFFF use at military

11 bases or by industrial PFAS emissions. The criteria for selecting study sites would include:

- 12 1. Documented past or present PFAS drinking water concentrations at the tap,
- 13 2. The magnitude of past or present PFAS concentrations at the tap,
- 14 3. Size of the population exposed,
- 15 4. Amount of information available on the contaminated drinking water system or private wells, and
- 16 5. If biomonitoring for PFAS has previously occurred at the site.

In order to determine the feasibility of a site for inclusion in the multi-site study, information on thefollowing parameters should be included in the application

 For public water systems using ground water sources, enumeration of supply wells that provided drinking water to the site. Information on each supply well should include years of operation, well capacity, and daily or monthly pumping rates. This information can be used to determine the monthly proportion of the total water supply provided by each well during the period when PFAS contamination occurred. Information is also necessary about changes to the water system (e.g., closure of contaminated supply wells) after the contamination was detected.

25 2. For a water system supplied by surface water, characteristics of this source.

- For a water system purchasing water from another system, characteristics of this source, the
 period of time purchased, and daily or monthly amount purchased in order to determine the
 proportion of the total water supply provided by the purchased water.

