The NCEH laboratory will perform the analyses of serum PFAS according to the biochemical analytical plan (Attachment 2) and approved laboratory methods (Kuklenyik 2015). The NCEH laboratory staff will also aliquot and ship blood and serum specimens to participating laboratories for the analyses of the effect biomarkers according to the plan. The recipient will store the urine samples and conduct analyses at a later date when more knowledge is gained about urinary PFAS and effect biomarkers and until the laboratory methods are developed. Residual blood and urines will be archived at NCEH so that additional PFAS or effect biomarkers can be analyzed as new knowledge and analytical methods become available.

23 3.6.5 Questionnaire

Each adult participant, and a parent of the child participant, will complete a questionnaire during theappointment for the blood draw.

26 3.6.5.1 Children and Parents

27 Study staff will request that the parents of the child participant complete the questionnaire. The 28 questionnaire will obtain demographic information (e.g., education, primary occupation), residential history, water consumption habits, medical history of the mother and child, the child's medications, the mother's reproductive history (including maternal age at birth of the participating child) and any occupational exposures the mother may have had to PFAS. The questionnaire will be administered in two formats: a form for the child whose parent is not also a participant (Attachment 15), and an abbreviated form for the child whose parent is also an adult participant (Attachment 15a).

6 The questionnaire will obtain the mother's and child's residential history in the study area, and the dates 7 and length of time of the pregnancy and breastfeeding of the child. The questionnaire will also obtain 8 information on the water consumption habits (including use of water for formula, juices, etc., bottled 9 water use) of the mother and child when they resided in the study area. Information on the mother's 10 workplaces in the study area (location and dates) and the child's daycare and schools in the study area 11 (location and dates) will be obtained.

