Section B: Residential History and Drinking Water Exposures

This next set of questions is about the child and the child's birth mother. If you are not her, we can follow up after this interview with a quick phone call to complete the questionnaire.

B1. What is the main source of tap water in your home?

____Public water system

____Private well

____Other: specify _____

____Don't know

_____Refused to answer

B2. On average, how many 8 oz. cups of tap water or beverages prepared with tap water does your child currently drink per day at home?

____ cups

____Doesn't drink tap water

____Don't know

____Refused to answer

Note: 1 cup = 8 oz.; 2 cups = 1 pint (16 oz.); 4 cups = 1 quart (32 oz.); 16 cups = 1 Gallon (128 oz.

B3. On average, how many 8 oz. cups of tap water or beverages prepared with tap water do you currently drink per day at home?

____ cups

____Doesn't drink tap water

____Don't know

Refused to answer

Note: 1 cup = 8 oz.; 2 cups = 1 pint (16 oz.); 4 cups = 1 quart (32 oz.); 16 cups = 1 Gallon (128 oz.

B4. What was your previous address?

Street	Apt	
City	State	Zip Code:

B5. When did you move into your previous address? Month____ Year_____

B6. What was the main source of tap water at that address?

____Public water system

____Private well

____Other: specify _____

____Don't know

_____Refused to answer

B7. On average, how many 8 oz. cups of tap water or beverages prepared with tap water did your child drink per day when living at your previous address?

____ cups

_Don't drink tap water

Don't know

____Refused to answer

____Your child did not live at this address

Note: 1 cup = 8 oz.; 2 cups = 1 pint (16 oz.); 4 cups = 1 quart (32 oz.); 16 cups = 1 Gallon (128 oz.

B8. Have you or your child lived at any other address since January 2000?

___Yes

__No → go to Section C

____Don't know \rightarrow go to Section C

____Refused to answer \rightarrow go to Section C

B9. Please fill out the table below for these other residences where you or your child lived since January 2000.

Street Address, City, State	Did your	Your child's average	Move in	Main source of
	child live	consumption of tap	(mm/yy)	tap water at
	at this	water per day (# cups)		this address
	address?	at this address		(public water
				system or
				private well?)

Note: 1 cup = 8 oz.; 2 cups = 1 pint (16 oz.); 4 cups = 1 quart (32 oz.); 16 cups = 1 Gallon (128 oz.

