Section B: Residential History and Drinking Water Exposures

B1. On average, how many 8 oz. cups of tap water or beverages prepared with tap water does your child currently drink per day at home?

____ cups

____Didn't drink tap water

____Don't know

____Refused to answer

Note: 1 cup = 8 oz.; 2 cups = 1 pint (16 oz.); 4 cups = 1 quart (32 oz.); 16 cups = 1 Gallon (128 oz.)

B2. Please fill out the table below for all residences that your child has lived.

Street Address, City, State	Your child's	Move in	Main source of
	average	(mm/yy)	tap water at
	consumption of		this address
	tap water per		(public water
	day (# cups) at		system or
	this address		private well?)

B3. When [you were/the child's birth mother was] pregnant with your child, on average how many 8

oz. cups of tap water or beverages prepared with tap water did [you/she] drink per day?

____ cups

___Didn't drink tap water

____Don't know

____Refused to answer

B4. When [you were/the child's birth mother was] breastfeeding your child, on average how many 8

- oz. cups of tap water or beverages prepared with tap water did [you/she] drink per day?
- ____ cups
- ____Didn't drink tap water
- ____Don't know
- ____Refused to answer
- ____Did not breastfeed my child

Section C: History of Potential Exposure Modifiers

This next set of questions is for the child's birth mother about the child. If you are not her, we can follow up after this interview with a quick phone call to complete the questionnaire.

- C1. Has your child ever had a blood transfusion?
- ____Yes ightarrow Please specify how many times your child had a blood transfusion______
- ___No →go to Question C3
- ___Don't know →go to Question C3
- ____Refused to answer →go to Question C3
- C2. When did your child last have a blood transfusion?

_____month/year

- C3. Has your child ever donated blood?
- ____Yes → Please specify how many times your child has donated blood______
- ___No \rightarrow go to Section D.
- ____Don't know \rightarrow go to Section D.
 - ___Refused to answer \rightarrow go to Section D.
- C4. When did your child last donate blood? _____ Month/Year

C5. On average, how often does your child donate blood in a year?

Section D: Occupational History of the Child

This next set of questions is for the child's birth mother about the child. If you are not her, we can follow up after this interview with a quick phone call to complete the questionnaire.

D1. Has your child been employed for at least one month at a job?

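### The long child form records tap-water intake at the present home only as current intake, with no move-in date, so intake there during the contaminated years is not collected

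*Protocol*

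**What the plan says.** Attachment 15 is completed when the child's parent is not also an adult participant; Attachment 15a when the parent is (Section 3.6.5.1).

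In Attachment 15, Section B:

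- B2, on the present home, asks "how many 8 oz. cups of tap water or beverages prepared with tap water does your child currently drink per day at home". One answer option is "Doesn't drink tap water".
- B7, on the previous address, asks how much "did your child drink per day when living at your previous address". B5 asks the move-in date for that address.
- B8 asks "Have you or your child lived at any other address since January 2000". Any answer other than yes skips to Section C.
- B9 then says "Please fill out the table below for these other residences where you or your child lived since January 2000", with columns for average intake and move-in date.

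In Attachment 15a, B2 reads "Please fill out the table below for all residences that your child has lived", with columns for the child's average intake, move-in date and water source at each address.

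Section 3.6.5.1 says the questionnaire will cover water habits "of the mother and child when they resided in the study area". Section 3.9 lists questionnaire data on contaminated-water consumption among the inputs to each participant's cumulative serum estimate. Section 3.10 makes that estimate the focus of the primary analyses and treats measured serum as supplemental.

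**The concern.** The primary exposure is a reconstruction of the past, so it needs intake while the water was contaminated. Section 3.2 admits people whose last exposure was up to 15 years before study start, and Section 2.3 anticipates changes such as closing contaminated wells after detection. Current intake may therefore postdate the exposure, reflect what the family did after learning of it, and belong to an older child. Eligible people are described as residing in a household in the target area, so the present home may well be the contaminated one. It is also the one home for which the long form asks nothing about the past.

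Two things are at stake. First, an input to the primary exposure is absent for long-form children who stayed in the affected home. Second, otherwise similar children get different inputs depending on whether a parent also enrolled as an adult, which has no necessary link to exposure. No later analysis decision can recover an answer that was never asked.

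**Working it through.** The plan states no figure that can be reproduced for this point. The check sets the items side by side and follows one type of child through both forms.

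**Step 1. Every intake item on the long form**

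| Item | Whose intake, where | Period |
|---|---|---|
| B2 | Child, present home | Now |
| B3 | Respondent, home | Now |
| B7 | Child, previous address | While living there |
| B9 | Child, other addresses since January 2000 | Average while living there |
| B10, B11 | Birth mother | Pregnancy, breastfeeding |
| D2 | Mother's workplace | Now |
| D5 | Child's job | While working |
| E2, E3 | Child, day care and school | While attending |

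Only B2 concerns the child at the present home, and no item asks whether or when tap-water drinking stopped. Move-in dates are asked for the previous address (B5) and the other addresses (B9). Section B has none for the present home, and no move-out date for the previous address from which it could be derived.

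**Step 2. Can another form fill the gap?** The long form is used when the parent is not an adult participant, so it has no parental adult questionnaire alongside it. The adult questionnaire (Attachment 16) is not in the text at hand and was not assessed.

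**Step 3. One child, two forms.** Take a child who has lived T years at the present home, drank d cups a day for the c years the supply was contaminated, then stopped. The reconstruction needs d for those c years.

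- Long form: B2 returns 0 cups or the non-drinker box. If B2 is carried back, direct home intake for the c years is 0 instead of d. If it is not carried back, that intake is missing. Without a move-in date, T is unknown as well.
- Short form: T is obtained. If the parent gives a literal time average, it is (d × c + 0 × (T − c)) / T = d × c / T, which is below d whenever c < T.

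The short form is better but still mixes the two periods.

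**Step 4. Does intake matter to serum?** Section 2.2 reports from Pease that "water consumption had the highest effect on PFHxS serum levels among persons aged" 19 or under, with coefficient 0.31 and marginal effect 36.4%. As a check, exp(0.31) − 1 = 36.3%, which agrees with the stated value to rounding. Geometric mean PFHxS was 4.76 µg/L for four or more cups a day and 3.77 µg/L for fewer than four: 4.76 / 3.77 = 1.26, or 26% higher. Both figures show that intake is associated with serum. Neither measures how far B2 departs from intake in the contaminated years.

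**The case against.** A reader might infer that the form records the contaminated years as non-drinking, or that affected children's exposure is 100% wrong. The documents support neither. B2 records present intake, and nothing tells the modeller to carry it back; Section 3.9 leaves the choice of model largely to the recipient. The zero arises only if B2 is carried back. Even then it covers only direct home intake, and only for children who stopped completely.

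Section 3.9 also uses measured serum, reconstructed water concentrations, NHANES background levels and pharmacokinetic models, and it plans to compare modelled with measured serum. A child with zero recorded intake and a high measured level could therefore be noticed. The mother's intake in pregnancy and breastfeeding, and the child's at day care and school, are asked historically. Where a well was closed and the family kept drinking tap water, current intake carries some information about the past.

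It is equally tempting to read the 36.4% and 26% as the size of the bias. They are associations of intake with serum at Pease, and the second is for all persons, not children.

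These arguments limit what can be claimed about size. They do not remove the gap: noticing a discrepancy does not supply the missing intake or move-in date, and the conflict with Section 3.6.5.1 and the difference between the two forms remain.

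**Conclusion.** The concern stands as a data-collection gap. Attachment 15 does not deliver what Section 3.6.5.1 promises for the child at the present home, and it gives the model less than Attachment 15a does. For a long-form child still living in the affected home, intake in the contaminated years is missing, or wrong if B2 stands in for it.

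The size cannot be estimated. The documents give neither the share of children who will be on the long form, nor how many stayed in an affected home, nor how many changed their drinking. If B2 is carried back for children who stopped, modelled exposure is pushed downward. That error could be differential if families in more contaminated or better-informed areas were likelier to stop, but the documents do not show that they were. Measured serum values are unaffected, though their analysis is supplemental. The conclusion rests on the item wording and on the role Sections 3.9 and 3.10 give to questionnaire intake.

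**What to change.** Change both child forms before they are fielded:

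- In Attachment 15, add the present home to the residence table, with its move-in date and the child's average cups of tap water per day there, and have every family complete that row whatever the answer to B8.
- Ask whether tap-water drinking at that home stopped or changed and, if so, the month and year, with cups per day before and after. Anchoring on the family's own date of change avoids needing contamination dates at interview. Section 1.1.3 says these may have to come from modelling; they can be applied later.
- Use the same before/after wording in the Attachment 15a table, whose single average per address blends the periods.
- State in Section 3.9 that the reconstruction uses intake for the relevant period, not B2.

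The cost is a few extra items, a small amount of interview time, and recall error in the date and the earlier intake. Recontacting families after fieldwork would mean longer recall.

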Attachment 15. Multi-site Study Child Questionnaire – Long Form

(best completed by the child's birth mother who is not an adult participant)

Form Approved OMB No. 0923-XXXX Exp. Date xx/xx/201x

ATSDR estimates the average public reporting burden for this collection of information as 30 minutes per response, including the time for reviewing instructions, searching existing data/information sources, gathering and maintaining the data/information needed, and completing and reviewing the collection of information. An agency may not conduct or sponsor, and a person is not required to respond to a collection of information unless it displays a currently valid OMB Control Number. Send comments regarding this burden estimate or any other aspect of this collection of information, including suggestions for reducing this burden to CDC/ATSDR Information Collection Review Office, [name]; ATTN: PRA (0923-xxxx).

Parent Study ID No.	
Child Study ID No.	

Section A: Demographic Information

- A1. What is your relationship to your child?
- ____Birth mother
- ____Birth father
- ____Adoptive mother
- ____Adoptive father
- ____Legal guardian
- ____Other relationship: specify ______
- ____Refused to answer
- A2. What is your child's sex?
- ___Male
- ____Female
- ____Refused to answer
- A3. What is your child's date of birth?
 - _____(MM/DD/YYYY)
- ____Refused to answer
- A4. Do you consider your child to be Hispanic or Latino?
 - __Yes
- No
- ____Refused to answer

- A5. What race do you consider your child to be? Mark all that apply.
- ____American Indian or Alaska Native
- ____Asian
- ____Black or African American
- ____Native Hawaiian or Other Pacific Islander
- ____White
- ____Refused to answer
- A6. What is the highest grade level of education your child has completed?
- ____grade
- A.7 What is the highest level of education you completed?
- Less than high school
- ____Some high school
- _____High school graduate or equivalent (GED)
- ____Some university/college
- ____Technical or trade school
- ____University/college graduate
- ____Graduate school or higher
- A8. What is the child's household income (from all sources)?
- ____Less than \$25,000
- ____\$25,000 to \$69,000
- ____\$70,000 to \$149,000
- ____More than \$150,000
- ____Don't know
- ____Refused to answer
- A9. During the last 12 months did the child have any kind of health insurance?
- ___Yes
- ___No
- ____Don't know
- ____Refused

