B10. When [you were/the child's birth mother was] pregnant with your child, on average how many 8 oz. cups of tap water or beverages prepared with tap water did [you/she] drink per day?

____ cups

____Didn't drink tap water

____Don't know

____Refused to answer

B11. When [you were//the child's birth mother was] breastfeeding your child, on average how many 8 oz. cups of tap water or beverages prepared with tap water did [you/she] drink per day?

- cups
- ____Didn't drink tap water
- ____Don't know
- ____Refused to answer
- ____Did not breastfeed my child

Section C: History of Potential Exposure Modifiers

This next set of questions is about the child and the child's birth mother. If you are not her, we can follow up after this interview with a quick phone call to complete the questionnaire.

- C1. [Have you/Has the birth mother] ever had a blood transfusion?
- ____Yes → Please specify how many times you had a blood transfusion______
- ___No →go to Question C3
- ____Don't know →go to Question C3
- ____Refused to answer →go to Question C3
- C2. When did [you/she] last have a blood transfusion? month/year
- C3. Has your child ever had a blood transfusion?
- ____Yes ightarrow Please specify how many times your child had a blood transfusion______
- ___No →go to Question C5
- ____Don't know →go to Question C5
- ____Refused to answer →go to Question C5
- C4. When did your child last have a blood transfusion?
- _____month/year
- C5. [Have you/Has the birth mother] ever donated blood?

___Yes

___No →go to Question C8

- ____Don't know →go to Question C8
- ____Refused to answer →go to Question C8
- C6. When did [you/the birth mother] last donate blood? _____ Month/Year

C7. On average, how often [do you/does the birth mother] donate blood in a year?

- C8. Has your child ever donated blood?
- ____Yes → Please specify how many times your child has donated blood______
- ___No \rightarrow go to Question D1.
- ____Don't know \rightarrow go to Question D1.
- ____Refused to answer \rightarrow go to Question D1.
- C9. When did your child last donate blood?
- _____ Month/Year

C10. On average, how often does your child donate blood in a year?

_____times

Section D: Occupational History

This next set of questions is about the child's birth mother. If you are not her, we can follow up after this interview with a quick phone call to complete the questionnaire.

D1. What is [your/the child's birth mother's] primary occupation?

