D2. On average, how many 8 oz. cups of tap water or beverages prepared with tap water do you currently drink per day at work?

____ cups

- ____Don't drink tap water
- ____Don't know
- ____Refused to answer

D3. Please fill out the table below for each job that lasted one month or more starting from the present and working back to 2000.

Job information	Job 1	Job 2	Job 3	Job 4
a. Where did the child's mother work				
(City, State)				
b. Name of the employer				
c. Start date (month, year)				
d. End date (month, year)				
e. Job title/description				
f. Did the child's mother work as a	Yes	Yes	Yes	Yes
firefighter?	No go to question g.	No go to question g.	No go to question g.	No go to question g.
If the child's mother worked as a	Yes	Yes	Yes	Yes
firefighter, did she come into contact	No	No	No	No
with firefighting foam used for fires	Don't know	Don't know	Don't know	Don't know
that involve flammable liquids (also				
known as class B fires)?				
g. was this job in any of the following	Manufacturing of nonstick	Manufacturing of nonstick	Manufacturing of nonstick	
Industries?	cookware	cookware	COOKWARE	COOKWARE
	yes no	yesno	yesno	yes10
	Manufacturing of stain resistant	contings used on cornets	contings used on cornets	contings used on carpots
	coatings used on carpets,	unbolstony and other fabrics	upholstony and other fabrics	upholstory, and other fabrics
	uphoistery, and other fabrics	ves no	ves no	
	yes10	Manufacturing of water resistant	Manufacturing of water resistant	Manufacturing of water resistant
	clothing	clothing	clothing	clothing
	yes no	yesno	yesno	yesno
h. Did the child's mother work with or		Yes (Please	Yes (Please	Yes (Please specify the chemical)
around any chemicals at this job such	Yes (Please specify the chemical)	specify the chemical)	specify the chemical)	
as solvents, metals, asbestos, or				No
pesticides?	No	No	No	Don't know
	Don't know	n't know	Don't know	
i. Did the child's mother work with	Yes	Yes	Yes	Yes
radiation?	No	No	No	No

Job information	Job 5	Job 6	Job 7	Job 8
a. Where did the child's mother work				
(City, State)				
b. Name of the employer				
c. Start date (month, year)				
d. End date (month, year)				
e. Job title/description				
f. Did child's mother work as a	Yes	Yes	Yes	Yes
firefighter?	No go to question g.	No go to question g.	No go to question g.	No go to question g.
If child's mother worked as a				
firefighter, did she come into contact	Yes	Yes	Yes	Yes
with firefighting foam used for fires	No	No	No	No

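### In the long-form child questionnaire, the residence and current water-intake items in sections about the birth mother ask only about the respondent, so a father or guardian can supply his own history in place of hers

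*Protocol*

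**What the plan says.** Section 3.6.5.1 of the protocol states that "The questionnaire will obtain the mother's and child's residential history in the study area", and that the mother's water habits while she lived there are obtained too. Attachment 15, the long form, is used when the child's parent is not also an adult participant. Its title line prefers the birth mother as respondent but does not require her. A1 offers birth father, adoptive mother or father, legal guardian and other relationship as alternatives.

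The introduction to Section B reads "This next set of questions is about the child and the child's birth mother". It adds that, if the respondent is someone else, staff may telephone afterwards so that the form can be finished. Section D opens in the same way, with the birth mother as its only subject.

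Inside those sections, B3 asks about drinks "prepared with tap water do you currently drink per day at home". B4 and B5 ask for the respondent's previous address and move-in date. B8 and B9 cover residences "where you or your child lived since January 2000". D2 asks about drinks "prepared with tap water do you currently drink per day at work". Other maternal items are worded differently. C1, for example, contains the bracketed choice "Have you/Has the birth mother] ever had a blood transfusion".

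**The concern.** The form's authors recognised that the respondent may not be the mother and wrote a birth-mother alternative into many items. They left it out of the items that establish where she lived. A father or guardian who sees the mother named in other items, and not in these, can reasonably answer them about himself.

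What is at stake is the exposure estimate. Section 3.9 lists questionnaire data among the inputs to each participant's estimated cumulative serum level, and section 3.10 makes that estimate the focus of the primary analyses. Section 5 hopes to use the modelling for vulnerable periods such as in utero exposure. Under section 3.2.1, in utero or breastfeeding exposure can itself qualify a child for the study. For that part of a child's history, the address that counts is the mother's.

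**Working it through.** No sample-size or power figure is involved, so the check is a comparison of wording.

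| Item | Content | Person addressed | Birth-mother alternative? |
|---|---|---|---|
| B3 | current home intake | respondent | no |
| B4-B5 | previous address, move-in date | respondent | no |
| B6 | water source at the B4 address | none named; follows B4 | not needed |
| B7 | child's intake at the B4 address | child | not needed; linked to B4 |
| B8-B9 | other residences since 2000 | respondent or child | no |
| B10-B11 | intake in pregnancy and breastfeeding | mother | yes |
| C1-C2, C5-C7 | transfusion, blood donation | mother | yes |
| D1 | occupation | mother | yes |
| D2 | current work intake | respondent | no |
| D3 | job table | mother, named as such | not needed |

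**Can the mother's pre-birth addresses be recovered from elsewhere on the form?**

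- B10-B11 ask how much she drank in pregnancy and while breastfeeding, but not where.
- Section G gives the pregnancy dates, without an address.
- D3 gives the city and state of her jobs, not her home.
- B9 lists places where the respondent or the child lived. It has a column for whether the child lived there and none for the mother. A home she had before the birth, without this respondent, is not requested.
- The short form (Attachment 15a) tabulates only the child's residences, so it offers no substitute.

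**Does the follow-up call repair this?** It is triggered by the respondent not being the mother, but it is permissive, and its stated purpose is to finish the form. An item already answered about the wrong person looks finished. A1 shows who answered, but not whether that person answered for himself or for her.

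**Which items bear on prenatal exposure?** Only the address items, B4-B5 and B8-B9. B3 and D2 ask about current intake. Answered by a non-mother, they misattribute present habits but do not alter the prenatal estimate.

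**Illustration only; the dates are chosen and are not in the documents.** The mother lives in the contaminated area from 2000, the father joins in 2012, and the child is born in 2013. Assume constant intake, no background exposure, and the half-lives in section 3.2.1 (about 3 years for PFOA and PFOS, about 5 for PFHxS). The fraction of steady state after t years is 1 − 2^(−t/half-life).

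- Mother's history, t = 13: 1 − 2^(−13/3) = 0.950 and 1 − 2^(−13/5) = 0.835.
- Father's history, t = 1: 1 − 2^(−1/3) = 0.206 and 1 − 2^(−1/5) = 0.129.
- Ratios: 0.950/0.206 = 4.6 and 0.835/0.129 = 6.5.

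The residence start date can thus dominate the water-derived maternal level at birth. With a different family history the error would be zero or would run the other way.

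**The case against.** The strongest reply is that the section introductions already name the birth mother as the subject, that D2 sits between two plainly maternal items, and that trained staff administer the form and could probe. A1 identifies every record answered by someone else, so those records can be flagged. No passage says a non-mother's answers will be entered as the mother's. Where respondent and mother shared addresses over the relevant years, nothing is lost. All of this stands, and it makes misrecording a risk and not a certain result. It does not supply addresses that were never asked for. The Manual of Procedures (Attachment 12), where an instruction to interviewers might sit, is still a placeholder.

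Stronger readings are tempting but are not supported:

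- A reader might infer from A7, "What is the highest level of education you completed", that maternal education is lost to the IQ and ADHD analyses. Section A is not introduced as maternal, and section 3.6.5.1 mentions education only as an example of demographic information.
- A reader might infer that the error is differential, because affected families also differ on neurobehavioral outcomes. The documents say nothing on this.
- A reader might take the 4.6-fold and 6.5-fold ratios as the expected error. They come from one chosen family and describe water-derived maternal serum at birth. The planned estimate also uses measured participant serum and NHANES background levels, and the effect on the child's cumulative estimate has not been computed.

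**Conclusion.** The wording gap is real, and it contradicts both section 3.6.5.1 and the introductions to Sections B and D. B3, B4-B5, B8-B9 and D2 can record a non-mother's history in place of the birth mother's. In those families her pre-birth addresses may not be collected at all, which would give the modelled serum a wrong or missing input for in utero and breastfeeding exposure.

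The size cannot be computed. The documents give neither the share of long-form respondents who are not the birth mother nor how often their addresses differ from hers. The conclusion assumes only that some such respondents take the items as printed and that their residence history differs from the mother's.

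**What to change.** 1. Put the birth-mother alternative already used in B10 into B3-B5, B8-B9 and D2. B6 needs no change.
2. Add a column to B9 asking whether the birth mother lived at each address, beside the existing column for the child.
3. Keep the child's own address history as a separate record, and tie B7 to it. If B4 is simply redirected to the birth mother, B7 would ask an adopted or guardian-raised child's intake at a home where the child may never have lived.
4. Where A1 is anything other than birth mother, make the planned call a required step for these items. If she cannot be reached, set the unanswered maternal items to missing and do not substitute the respondent's history.

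The cost is some rewording, one column, a separate child address record where needed, and a procedural rule. The form still carries placeholder approval numbers, and the call is already foreseen. Recovering uncollected addresses after fieldwork would mean contacting families again.
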